3.12.3.2 Cardiac Valvular Toxicity Stopping Criteria

Subjects who have a new asymptomatic, moderate regurgitation or stenosis by echocardiogram (ECHO) (Grade 2 mitral/tricuspid/aortic valvular toxicity per National Cancer Institute-Common Toxicity Criteria for Adverse Events [NCI-CTCAE], version 4.03) should temporarily discontinue study treatment (both trametinib and dabrafenib if on combination therapy) and have a repeat evaluation by ECHO within 1 week. ECHO should be repeated every 1 to 2 weeks for 4 weeks or until valve recovery to baseline.

- If the valve recovers to baseline any time during the next 4 weeks, the subject may be restarted on study treatment at a reduced dose(s) (see Appendix 2 dosing nomogram “Dose Reduction” columns for trametinib and dabrafenib). For such subjects, monitoring of the valve via ECHO will then be performed 2 and 4 weeks after rechallenge, and every 4 weeks thereafter for 16 weeks and then per protocol.
- If repeat ECHO does not reveal valve recovery to baseline within 4 weeks, then the subject should permanently discontinue study treatment (both trametinib and dabrafenib if on combination therapy). The valve should continue to be monitored via ECHO every 4 weeks for 16 weeks or until resolution.

Subjects with a Grade 3 or 4 (symptomatic, severe regurgitation/stenosis by imaging with symptoms controlled by medical intervention) valvular toxicity must discontinue study treatment (both trametinib and dabrafenib if on combination therapy). Valvular toxicity should continue to be monitored every 4 weeks for 16 weeks or until resolution. If recovery occurs (return to baseline via imaging AND symptom resolution) within 4 weeks, the subject may restart study treatment at a reduced dose (see Appendix 2 dosing nomogram “Dose Reduction” columns for trametinib and dabrafenib).

ECHO must be performed at baseline and at the final study visit. Copies of all ECHO(s) and cardiology consultations performed on subjects who experience valvular toxicity will be

required by Novartis for review. Instructions for submitting qualifying ECHOs are provided in the Study Procedures Manual (SPM).

3.13 Dose Delay and Modification for Events Considered Related to Trametinib

A maximum of one trametinib dose reduction is allowed. If a second dose level reduction is required, treatment will be permanently discontinued.

Trametinib dose modification guidelines are outlined in [Table 3-6](#) for clinically significant toxicities with exception for following events of special interest:

- rash ([Section 3.13.3](#))
- diarrhea ([Section 3.13.4](#))
- ejection fraction changes ([Section 3.12.3.1](#))
- hypertension ([Section 3.13.5](#))
- prolonged QTc ([Section 3.12.1](#))
- pneumonitis ([Section 3.13.5](#))
- visual changes ([Section 3.13.5](#))
- liver chemistry elevation ([Section 3.12.1](#))

For these refer to the relevant sections for dose modification guidelines for adverse events of special interest as stated above.

If treatment related toxicities occur when dabrafenib is used in combination with trametinib then both treatments should be simultaneously dose reduced, interrupted or discontinued with the exceptions described below.

3.13.1 Dose Delay and Modification for Events Considered Related to Trametinib and/or Dabrafenib

Table 3-6 Dose Delay and Modification for General Events Considered Related to Trametinib and/or Dabrafenib

CTCAE Grade	Recommended adverse event management guidelines	Mandatory dose modification requirements
Grade 1 and tolerable Grade 2	
 • Monitor closely • Provide supporting care according to institutional standards 	
 • Continue study drug(s) at current dose level
Intolerable Grade 2 and Grade 3	
 • Monitor closely. • Provide supportive care according to institutional standards. 	
 • Interrupt study drug(s) (except for cuSCC, keratoacanthoma, new primary melanoma, and basal cell carcinoma) • When toxicity resolves to Grade 1 or baseline, restart study drug(s) at reduced levels (see Appendix 2 dosing nomogram "Dose Reduction" columns for trametinib and dabrafenib) • If the Grade 2 (intolerable) or Grade 3 toxicity recurs while at reduced dose, discontinue study treatment(s) • If the Grade 2 (intolerable) or Grade 3 toxicity recurs while after re-escalating to previous dose,

CTCAE Grade	Recommended adverse event management guidelines	Mandatory dose modification requirements
		
 Interrupt dabrafenib and trametinib. When toxicity resolves to Grade 1 or baseline, restart study drug(s) reduced levels (see Appendix 2 dosing nomogram "Dose Reduction" columns for trametinib and dabrafenib)
Grade 4	
 Monitor closely. Provide supportive care according to institutional standards. 	
 Interrupt study drug (s) Once toxicity resolves to \leq Grade 1 or baseline, restart study drug(s) at reduced levels (see Appendix 2 dosing nomogram "Dose Reduction" columns for trametinib and dabrafenib) or permanently discontinue study drug (s) at the discretion of investigator

Table 3-6a Dose Modification for dabrafenib (DRB436) dispersible tablet for patients less than 12 years of age

Weight (kg)	Dose (b.i.d)	Dose Reduction Level 1 (b.i.d)	Dose Reduction Level 2 (b.i.d)
7-9.5	20 mg	10 mg	0 mg
9.6-13.5	30 mg	20 mg	10 mg
13.6-17.5	40 mg	30 mg	20 mg
17.6-20.5	50 mg	40 mg	30 mg
20.6-24.5	60 mg	50 mg	40 mg
24.6-28.5	70 mg	60 mg	50 mg
28.6-32.5	80 mg	70 mg	60 mg
32.6-36.5	90 mg	80 mg	70 mg
36.6-40.5	100 mg	90 mg	80 mg
40.6-43.5	110 mg	100 mg	90 mg
43.6-47.5	120 mg	110 mg	100 mg
47.6-51.5	130 mg	120 mg	110 mg
51.6-55.5	140 mg	130 mg	120 mg
\geq 55.6 kg	150 mg	140 mg	130 mg
Dose: 5.25 mg/kg/day Dose level 1: 4.5 mg/kg/day Dose level 2: 3.75 mg/kg/day			

Table 3-6b Dose Modification for dabrafenib (DRB436) dispersible tablet for patients greater or equal 12 years of age

Weight	Dose (b.i.d)	Dose Reduction Level 1 (b.i.d)	Dose Reduction Level 2 (b.i.d)
10-11.5	20 mg	10 mg	0 mg
11.6-17.5	30 mg	20 mg	10 mg
17.6-20.5	40 mg	30 mg	20 mg
20.6-24.5	50 mg	40 mg	30 mg
24.6-28.5	60 mg	50 mg	40 mg
28.6-32.5	70 mg	60 mg	50 mg
32.6-36.5	80 mg	70 mg	50 mg

36.6-40.5	90 mg	80 mg	60 mg
40.6-43.5	100 mg	90 mg	60 mg
43.6-47.5	110 mg	100 mg	70 mg
47.6-51.5	120 mg	110 mg	80 mg
51.6-55.5	130 mg	120 mg	80 mg
55.6-64.5	140 mg	130 mg	100 mg
≥64.6	150 mg	140 mg	110 mg
Dose: 4.5 mg/kg/day Dose level 1: 3.75 mg/kg/day Dose level 2: 3.00 mg/kg/day			

For subjects treated with solid dosage forms, dose reductions will occur in increments of 50 mg from the total daily dose for dabrafenib capsules and in increments of 0.5 mg from the total daily dose for trametinib tablets. See also [Appendix 2](#).

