3.2.3.1 Non-Hematological Dose Limiting Toxicity

- Any Grade 4 non-hematological toxicity with the exception of
 - Grade 4 fever/pyrexia that resolves to grade <2 within 72 hr with supportive care (anti-pyretics)
- Any Grade 3 non-hematological toxicity with the specific exclusion of:
 - Grade 3 nausea and vomiting of less than 3 days duration,
 - Grade 3 fever or infection of less than 7 days duration,
 - Grade 3 hypophosphatemia, hypokalemia, hypocalcemia or hypomagnesemia responsive to oral supplements within 7 days,
- Dose limiting hypertension will be considered as the following:
 - Grade 4 hypertension

- Any Grade 2 non-hematological toxicity that persists for greater than or equal to 7 days and is considered medically significant or sufficiently intolerable by subjects that it requires treatment interruption.
 - Grade 2 allergic reactions that necessitate discontinuation of study treatment will not be considered a dose-limiting toxicity
- Grade 2 left ventricular ejection fraction decrease (see [Section 3.12.3.1](#))
- Grade 2 cardiac valvular toxicity (mitral/aortic/tricuspid) (see [Section 3.12.3.2](#))
- Grade 2 diarrhea (see [Section 3.13.4](#))
- Grade 2 pneumonitis (see [Section 3.13.7](#))
- Treatment interruption longer than 14 days due to delayed recovery from toxicity will be dose limiting. Treatment delays for non-hematological toxicity ([Section 3.6](#)) that exceed 28 days meet the criteria for permanent discontinuation of study treatment ([Section 6.3](#)).

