3.2.3.2 Hematological Dose Limiting Toxicity

- Any hematologic toxicity requiring treatment interruption for greater than 14 days or requires a dose reduction. Treatment delays for hematological toxicity ([Section 3.6](#)) that exceed 28 days meet the criteria for permanent discontinuation of study treatment ([Section 6.3](#)).
- Grade 4 neutropenia on 2 consecutive measurements at least 72 hr apart (continue study treatment for first measurement of Grade 4 neutropenia, recheck within 72 hr, if Grade 4 neutropenia confirmed then hold study treatment and declare as DLT)
- Grade 4 thrombocytopenia or Grade 3 thrombocytopenia requiring platelet transfusion (exception: prophylactic platelet transfusions for platelet count $\geq 25,000$ administered prior to procedures will not be considered dose limiting)
- Grade 4 anemia
- Grade 3 or 4 hemolysis
- Grade ≥ 3 leukopenia is not a dose-limiting toxicity in the absence of dose-limiting neutropenia (see above).
- Grade ≥ 3 lymphopenia will not be considered dose limiting.
- Grade ≥ 3 decrease in hemoglobin that can be corrected to at least 8.0 g/dL (Grade 2) by transfusion of red blood cells is not a dose-limiting toxicity

Maximum Tolerated Dose

The MTD is the highest dose at which no more than 1 out of 6 subjects (or $< 33\%$) experience DLT during the first 28 days of therapy. If 2 or more subjects in a dosing cohort of 3-6 subjects (or $\geq 33\%$) experience DLT, the MTD has been exceeded.

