3.6 Criteria for Continuing in the Study

For subjects enrolled on Part A, Part B, Part C, and Part D, the following criteria must be met to advance beyond the first 28 days:

- Subjects have not met discontinuation of treatment criteria ([Section 6.3](#))
- No evidence of progressive disease (See [Section 7.6](#)) defined as no clinical evidence of progression for assessments that do not require imaging/disease assessment or no evidence of radiographic or histologic/morphologic progression if disease assessment included imaging (solid tumor)

Patients will be permitted to continue study treatment beyond initial Investigator-assessed disease progression, as long as they meet the following criteria:

- Investigator assessed clear evidence of clinical benefit
- Tolerance of study drug
- Continuation of study treatment is in the best interest of the patient as determined by the Investigator. For this determination, the investigator should consider all relevant data, such as:

- Absence of symptoms and signs of progressive disease
- No decline in performance status
- Absence of rapid progression of disease or of progressive tumor at critical anatomic sites (e.g., cord compression) that would require urgent medical intervention.
- Patient/guardian is willing to continue on the study

If the Investigator determines that all above criteria are met, the patient may continue study treatment and follow all study related procedures, including tumor assessments, as scheduled in the appropriate Time and Events Tables ([Section 7.1](#) table).

- After each tumor assessment, the investigator must confirm if the patient is still benefitting from study treatment, and document this in patient medical records. Toxicity resolved to baseline or grade ≤ 2 with specific exception of:
 - Specific criteria for Ejection Fraction Results ([Section 3.12.3](#)).
 - For subjects in Part B who are not evaluable for hematological toxicity due to marginal bone marrow function from disease infiltration or prior therapy, the following hematologic criteria must be met:
 - Absolute neutrophil count > 500 cell/ μ L,
 - Platelet count $> 25,000/\mu$ L (without transfusion in ≥ 7 days),
 - No life threatening consequences of anemia (no grade 4 anemia per NCI-CTCAE v4.03) ([NCI 2009](#)).

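### Section 3.2.3.2 and Table 3-6 conflict on haematological toxicity, so an unconfirmed Grade 4 neutropenia and some Grade 3 cytopenias are a DLT on one reading and not on the other

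*Protocol*

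**What the plan says.** **First Grade 4 neutropenia.** Protocol Section 3.2.3.2 tells the site to "continue study treatment for first measurement of Grade 4 neutropenia", to recheck, and to hold and declare a DLT only if Grade 4 is confirmed. The same bullet requires the two values to be separated by no less than 72 hours, yet sets 72 hours as the latest time for the recheck. Table 3-6 (Section 3.13.1), in its mandatory column, has study drug interrupted at Grade 4. On recovery to Grade 1 or baseline the drug is either restarted at a reduced level or stopped for good, at the investigator's discretion.

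**Grade 3 events.** For intolerable Grade 2 and for Grade 3, the mandatory column of Table 3-6 reads "When toxicity resolves to Grade 1 or baseline, restart study drug(s) at reduced levels". Section 3.13 lists the events exempt from the table: rash, diarrhoea, ejection fraction changes, hypertension, QTc, pneumonitis, visual changes and liver chemistry. No haematological event is among them.

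**What counts as a haematological DLT.** Section 3.2.3.2 opens with "Any hematologic toxicity requiring treatment interruption for greater than 14 days or requires a dose reduction". It then gives specific entries, such as confirmed Grade 4 neutropenia and Grade 3 thrombocytopenia that needs a platelet transfusion, and some express exclusions.

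**Length of a hold.** Section 3.2.3.1 states "Treatment interruption longer than 14 days due to delayed recovery from toxicity will be dose limiting". Neither DLT section gives a grade at which a hold ends. Both cite Section 3.6 beside treatment delays. That section has "Toxicity resolved to baseline or grade ≤ 2 with specific exception of" certain listed cases, under the introduction "the following criteria must be met to advance beyond the first 28 days".

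**The concern.** A site that sees one Grade 4 neutrophil value in the DLT period cannot both continue and interrupt. The choice also carries over into the DLT count, because the reduced-dose restart that Table 3-6 requires is itself a haematological DLT under the opening clause of 3.2.3.2. By the same route, Grade 3 events that the specific list leaves out become DLTs.

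The DLT count decides whether a dose is declared tolerable. Two or more DLTs in three to six children mean that the MTD is exceeded (Sections 3.2.2 and 3.2.3.2). The same threshold governs 0.032 mg/kg/day alone (Section 3.2.6) and with dabrafenib (Section 3.4.1). A definition that gives two answers for one child can therefore give two answers for a dose level.

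**Working it through.** **Step 1. The two routes compared.** Take an event in the first 28 days of a dose-determining cohort that is judged related.

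| Event | Specific list in 3.2.3.2 | Table 3-6, then the reduction clause of 3.2.3.2 |
|---|---|---|
| One Grade 4 neutrophil value, not confirmed | Drug continues; no DLT | Interrupt; if restarted, at a reduced dose: DLT |
| Grade 4 neutropenia, confirmed | DLT | DLT |
| Grade 3 neutropenia | Not listed | Interrupt, restart reduced: DLT |
| Grade 3 thrombocytopenia, no platelet transfusion | Not listed | Interrupt, restart reduced: DLT |
| Grade 4 thrombocytopenia | DLT | DLT |
| Grade ≥3 lymphopenia; leukopenia without dose-limiting neutropenia; haemoglobin fall corrected by transfusion | Expressly excluded | Exclusion taken to stand |

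The first, third and fourth rows change status with the reading.

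**Step 2. The recheck interval.** No less than 72 hours apart and no later than 72 hours are both met only at exactly 72 hours. A confirming value at 48 hours satisfies the instruction to recheck but not the required spacing.

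**Step 3. Effect on the dose decision.** With one DLT among six, 1/6 is tolerated. One reclassified child gives 2/6, and the MTD is exceeded.

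Table 12-1 (Section 12.2.1) shows how the 3+3 rule responds to the DLT rate p. The formula is P(escalate) = (1−p)³ + 3p(1−p)² × (1−p)³.

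- p = 0.10: 0.729 + 0.177 = 0.906 (table: 0.91)
- p = 0.20: 0.512 + 0.197 = 0.709 (table: 0.71)
- p = 0.30 to 0.60: 0.494, 0.309, 0.172, 0.082 (table: 0.49, 0.31, 0.17, 0.08)

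The table reproduces in all six columns. The protocol does not say how often the affected events occur. If, as an assumption, the wider reading added 5 to 15 percentage points to p, P(escalate) would fall from 0.906 to between 0.814 and 0.600 at a 10% base rate. At a 20% base rate it would fall from 0.709 to between 0.600 and 0.396.

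**Step 4. The end of a hold (lesser point).** The times here are assumed. A toxicity that reaches Grade 2 on hold day 6 and Grade 1 on day 18 is a 6-day hold if Grade ≤2 ends it and an 18-day hold if Grade 1 does; only the second exceeds 14 days. With days 20 and 32, only the second exceeds 28 days. Few DLT classifications turn on this. A haematological hold restarted under Table 3-6 is a DLT through the reduction, whatever its length. Most Grade 3 and nearly all Grade 4 non-haematological events are DLTs already. The 14-day rule matters mainly for the Grade 3 events that 3.2.3.1 excludes: brief nausea and vomiting, short fever or infection, and correctable electrolyte changes.

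**Step 5. Who is still affected.** The Amendment 9 rationale gives 139 treated, 80 discontinued and 13 moved to the rollover study as of 17-Jul-2020. That leaves 139 − 80 = 59 on treatment if the 13 are among the 80, or 59 − 13 = 46 if they are not.

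**The case against.** The best defence is that the specific rule prevails. Section 3.13 confines Table 3-6 to clinically significant toxicities. Section 3.14, describing the same table, says that it serves events without their own guideline and calls for clinical judgement. The neutropenia instruction in 3.2.3.2 can be seen as such a guideline. This softens the conflict but does not remove it: the table's column is headed mandatory, and the exemption list in 3.13 names no haematological event. Leaving the matter to judgement also leaves DLT status to the individual investigator.

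Several stronger readings are tempting, and the protocol does not support them:

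- *Section 3.6 and Table 3-6 are opposed restart rules.* Section 3.6 is a gate for going past Day 28. It is compatible with the table, which itself lets a tolerable Grade 2 go on with "Continue study drug(s) at current dose level". The problem is a cross-reference to 3.6 and no stated end of a hold.
- *The neutropenia conflict makes the 14- and 28-day clocks stop at different times.* It decides whether a hold starts.
- *Every Grade 3 cytopenia becomes a DLT.* The exclusions in 3.2.3.2 prevent that.
- *The rash table (Table 3-7) contradicts itself.* Its two recovery grades serve two different decisions, restart and discontinuation.

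**Conclusion.** The conflict between 3.2.3.2 and Table 3-6 stands for three kinds of event: an unconfirmed Grade 4 neutropenia, a related Grade 3 neutropenia, and a related Grade 3 thrombocytopenia without transfusion. For the first, the treatment instruction and, where drug is restarted, the DLT status both differ. For the other two, the DLT status differs. The 72-hour wording contradicts itself. The missing recovery grade for the 14- and 28-day rules is a real but smaller gap, and Section 6.3 makes discontinuation after 28 days permissive.

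One child is enough to change a cohort's result, but only if a cohort already had one DLT and such an event occurred. The protocol does not report either by cohort, so a reader should not infer that any declared dose is wrong. All cohorts had closed by Amendment 9 and the recommended doses had been declared, so the effect on the DLT count is retrospective. Table 3-6 still governs the children on treatment, and nothing says whether the 3.2.3.2 instruction lapses after Day 28, so the management conflict remains. The SAP was not available. A counting convention there could settle the classification, but not what sites are told to do.

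**What to change.** 1. Reconcile Section 3.2.3.2 and Table 3-6 on a first Grade 4 neutropenia, and the two statements of the recheck interval, as the clinical team decides.
2. State whether a reduction made only because Table 3-6 mandates it counts as a haematological DLT.
3. State which section's recovery grade ends a hold for the 14- and 28-day rules.
4. In the report, list every DLT-period hold or reduction in the dose-determining cohorts whose DLT status depends on the reading, and give the cohort's DLT count under each reading.

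The cost is a protocol clarification and one listing check of data that the case report form already collects (treatment delays and dose reductions, Section 4.4). No new data and no change to the design are needed.

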3.13.2 Guidelines and Dose Modifications for Trametinib Events of Special Interest

The severity of adverse events (AEs) will be graded utilizing the NCI-CTCAE v4.03 ([NCI 2009](#)). Guidelines for dose modifications and interruptions for management of common toxicities associated with trametinib are provided in this section.

3.13.3 Management of Rash

Rash is a frequent AE observed in subjects receiving trametinib and dabrafenib (see the Investigator’s Brochure for more information). A proactive approach is recommended. Encourage subjects to avoid unnecessary exposure to sunlight and encourage use of sunscreens and sunblock (see [Section 3.13.3.1](#)). If subjects develop rash, verify treatment intervention and consider recommended steps outlined under [Section 3.13.3.2](#) and [Table 3-7](#).

3.13.3.1 Prophylactic Treatment

The following management should be considered (see [Table 3-7](#)). The prophylactic regimen should be based on the investigator’s experience.

1. Broad-spectrum sunscreen (containing titanium dioxide or zinc oxide) with a skin protection factor (SPF) ≥15 at least twice daily.
2. Thick, alcohol-free emollient cream (e.g., glycerine and cetomacrogol cream) on dry areas of the body at least twice daily.
3. Mild strength topical steroid (e.g., hydrocortisone 1% cream) and topical antibiotics (e.g. clindamycin) applied at least twice daily starting on Day 1 of study treatment, to body areas such as face, chest and upper back with escalation to higher strength and/or oral steroid as detailed below.
4. Offer doxycycline or minocycline for 2 to 3 weeks of study treatment administration. May dose per institutional guidelines or substitute similar antibiotic. Consider topical antibiotics if oral doxycycline or minocycline is not feasible or tolerable.

- Doxycycline:
 - No dosing recommendations for children < 8 years of age
 - Children < 45 kg: 2.2 mg/kg/dose PO twice daily
 - Children ≥ 45 kg: 100 mg PO twice daily
- Minocycline:
 - No dosing recommendations for children < 8 years of age
 - Children < 45 kg: 2 mg/kg/dose PO twice daily
 - Children ≥ 45 kg: 100 mg PO twice daily

3.13.3.2 Reactive Management

It is strongly recommended that subjects who develop rash/skin toxicities receive evaluations for management of the specific side effect.

- For **pruritic lesions**, the use of cool compresses and oral antihistamine agents may be helpful.
- For **fissuring**, the use of Monsel’s solution, silver nitrate or zinc oxide cream is advised.
- For **desquamation**, thick emollients and mild soap are recommended.
- For **paronychia**, antiseptic bath and local potent corticosteroids in addition to oral antibiotics are recommended, and if no improvement is seen, a dermatology or surgery consultation is recommended.
- For **infected lesions**, bacterial and fungal culturing followed by the appropriate culture-driven systemic or topical antibiotics is indicated.

Table 3-7 Mandatory dose modifications and recommended clinical management guidelines for rash

CTCAE v4.03 Grade	Recommended adverse event management guidelines	Mandatory dose modification requirements
Grade 1 (Rash covering < 10% body surface area)	
 • Initiate prophylactic and symptomatic treatment measures • Consider use of topical corticosteroids or urea containing creams in combination with oral antipruritics or moderate strength topical steroid (hydrocortisone 2.5% cream or fluticasone propionate 0.5% cream) • Reassess after 2 weeks 	
 • Continue study drug(s) • If rash does not recover to baseline within 2 weeks despite best supportive care, reduce study drug (s) dose (see Appendix 2 dosing nomogram “Dose Reduction” columns for trametinib and dabrafenib)
Grade 2 (10-30% of body surface area)	If tolerable, as per Grade 1: 
 • Initiate prophylactic and symptomatic treatment measures for first 6 weeks of study treatment • Use moderate strength topical steroid (hydrocortisone 2.5% cream or fluticasone propionate 0.5% cream) • Reassess after 2 weeks. 	
 • Reduce study drug (s) dose (see Appendix 2 dosing nomogram “Dose Reduction” columns for trametinib and dabrafenib) • If rash recovers to ≤Grade 1 within 2 weeks, increase dose to previous dose level • If no recovery to ≤Grade 1 within 2 weeks, interrupt study drug(s) until recovery to ≤grade 1, restart study drug (s) at reduced dose (see Appendix 2 dosing nomogram “Dose Reduction” columns for trametinib and dabrafenib)
Grade ≥3 (More than	Use moderate strength topical steroids (PLUS consider a brief period of oral high	
 • Interrupt study drug(s) until rash recovers to Grade ≤1 • Restart with study drug(s) at reduced dose level (see

CTCAE v4.03 Grade	Recommended adverse event management guidelines	Mandatory dose modification requirements
30% of body surface area or Life-threatening)	dose steroid such as methylprednisolone) Consult dermatologist	Appendix 2 dosing nomogram “Dose Reduction” columns for trametinib and dabrafenib) 
 Escalation of study drug (s) to previous dose level may be considered if no rash is evident 4 weeks after restarting study treatment If no recovery to grade ≤2 within 4 weeks, permanently discontinue study drug(s). NOTE: suspected cases of SCAR require permanent discontinuation of study treatment, see section 3.13.3.3

